1.2.4 Evaluate the PSA doubling time
Endpoint: Time elapsed from baseline PSA to double in value.

1.2.5 Evaluate overall survival at 2 years relative to the SWOG intermittent ADT historic cohort.
Endpoint: Patients will be followed for survival for two years after study enrollment

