2 BACKGROUND

Background: Prostate cancer is the most commonly diagnosed cancer in the United States and second leading cause of cancer death. At diagnosis, approximately 10% of men will have bone metastases identified on technetium bone scan [1]. These bone metastases can result in skeletal related events (SREs) causing substantial morbidity [2]. Men with five or fewer prostate cancer bone metastases noted on initial bone scan have a 94% 2-year survival rate, and a significantly favorable overall survival when compared to those with more lesions [3]. The current standard of care for men with overt metastatic disease is immediate androgen deprivation therapy (ADT) [4]. Long term androgen deprivation therapy results in a significant decrement in quality of life[5] and a host of unfavorable side effects including but not limited to loss of libido, lack of energy, difficulty concentrating, hot flashes, decreased bone density, decreased muscle mass, and increased risk of heart attack and stroke. Although ADT will delay the appearance of tumor related symptoms in metastatic patients, there are no data that it prolongs overall survival[4]. Developing novel strategies to control metastatic prostate cancer with side effect profiles superior to that of ADT or other approved systemic agents is highly desirable. External beam radiation treatment is effective at controlling both primary and metastatic prostate cancers, and Radium-223 has demonstrated a survival benefit in castrate-resistant prostate cancers. Both forms of therapy have been shown to palliate painful bony lesions.

Rationale for the combination of Radium-223 and External Beam Radiation: Radium-223 is a calcium-mimetic radiopharmaceutical that accumulates in bones and emits alpha radiation from Radium-223 decay and releases relatively high energy with a narrow range (2 to 10 cells)[5]. Following promising results in a phase II trial, the phase III ALSYMPCA trial was conducted in mCRPC with symptomatic bone metastases who either had received or were ineligible for docetaxel [6, 7]. Patients received 6 doses of Radium-223 50 kBq/kg intravenously every 4 weeks. A pre-planned interim analysis showed a significant 2.8-month median OS benefit compared to the placebo arm (14 vs. 11.2 months), which is anticipated to lead to regulatory approval [8]. An updated analysis

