In 2012 the SWOG cooperative group reported mature results of a randomized trial evaluating continuous versus intermittent androgen-deprivation therapy in men with hormone-naïve metastatic prostate cancer [14]. This trial was pivotal in cementing the care standard of immediate and continuous androgen deprivation in men with hormone-naïve metastatic prostate cancer, as a median survival benefit was noted over the intermittent cohort despite the fact that, statistically speaking, inferiority of intermittent therapy was not proven nor disproven. Men on the intermittent therapy arm did have significant improvement in quality of life domains. Notably, 78% of persons on the “intermittent” androgen therapy arm had to resume ADT within the first 15 months. Additionally, the investigators of this study classified patients as having “minimal” versus “extensive” disease as an analysis stratification. Minimal disease was defined as disease confined to the spine, pelvic bones, or lymph nodes. Those with visceral metastasis or other bony sites were classified as extensive. At 2 years, subjects with “minimal disease” receiving intermittent androgen deprivation had an 85% overall survival. We propose using the intermittent ADT cohort of the SWOG trial as a historic comparator of efficacy to this study.

Oligometastasis is a limited disease state that some have postulated may be curable. We will use best available ablative therapies to destroy gross tumor, and allow radium-223 to obliterate occult sites of metastasis that cannot be resolved by available imaging modalities. This may lead to delay of initiation of ADT or other antineoplastic systemic therapies, improved QOL, survival benefit, and potential cure.

Reference treatment is the standard of care use of immediate and continuous ADT as well as other reasonable standards of intermittent ADT, or other antineoplastic systemic therapies. Hypofractionated radiotherapy is not routinely used in asymptomatic lesions unless there is risk of impending pathologic injury.

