4 STUDY DESIGN

4.1 Description

This is a phase IIa, open-label, single-arm, and prospective study of hormone therapy-naïve men with oligometastatic prostate cancer to the bone. The study will test if treating the primary tumor sites and 5 or fewer sites of bone-only metastasis with external beam radiation with concomitant systemic Radium-223 will reduce the utilization of androgen deprivation therapy, improve QOL and improve OS over the comparator cohort of SWOG intermittent ADT historic cohort.

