5.1 Inclusion Criteria

Yes/No (Response of "no" = patient ineligible)

5.1.1 _____ Asymptomatic or symptomatic hormone naïve men with testosterone levels ≥ 100 ng/dL with previously treated localized prostate cancer who now have rising PSAs and five or fewer bone metastases.

5.1.2 _____ Subjects who have been previously treated with definitive and/or adjuvant/salvage radiotherapy to the primary site and/or regional lymph nodes with concurrent ADT are allowed if the last hormone therapy delivered > 6 months prior. Subjects who have had more than 30 days and fewer than 45 days of bicalutamide monotherapy for any reason within the 6 months prior to enrollment are eligible for the study, providing they have been off of the drug for at least 30 days prior to enrollment. Subjects who have had fewer than 30 days of bicalutamide are eligible for the study, as long as they discontinue the drug at least 5 days prior to the first study treatment.

5.1.3 _____ Histologic confirmation of Prostate Adenocarcinoma diagnosis.

5.1.4 _____ Age ≥ 18 years.

5.1.5 _____ Life expectancy of at least 2 years.

5.1.6 _____ Acceptable hematology and serum biochemistry screening values:

- White Blood Cell Count (WBC) $\geq 3,000/\text{mm}^3$
- Absolute Neutrophil Count (ANC) $\geq 1,500/\text{mm}^3$
- Platelet (PLT) count $\geq 100,000/\text{mm}^3$
- Hemoglobin (HGB) $\geq 10 \text{ g/dL}$
- Total bilirubin level $\leq 1.5 \times$ institutional upper limit of normal (ULN)
- Aspartate aminotransferase (AST) and alanine aminotransferase (ALT) $\leq 2.5 \times$ ULN
- Creatinine $\leq 1.5 \times$ ULN
- Albumin $> 2.5 \text{ mg/dL}$

5.1.7 _____ Willing and able to comply with the protocol, including follow-up visits and examinations.

5.1.8 _____ Karnofsky Performance Score >60 or ECOG equivalent.

5.1.9 Radiographic confirmation of oligometastatic diagnosis via Bone Scan validated by either CT scan, or MRI or PET/CT with Fluciclovine within the past 90 days.

5.1.10 Subjects who have not had surgical removal of their prostate and have a partner of child bearing potential must agree to use condoms beginning at the signing of the ICF until at least 6 months after the last dose of study drug. Because of the potential side effect on spermatogenesis associated with radiation, female partners of childbearing potential must agree to use a highly effective contraceptive method during and for 6 months after completing treatment.

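### The 2-year survival comparison with SWOG uses a cohort not matched on lesion count, so an apparent survival gain could come from population differences alone

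*Combined protocol and SAP*

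**What the plan says.** Objective 1.2.5 is to "Evaluate overall survival at 2 years relative to the SWOG intermittent ADT historic cohort", with the endpoint "Patients will be followed for survival for two years after study enrollment". Section 4.1 goes further and lists, among the things the study will test, whether treatment will "improve QOL and improve OS over the comparator cohort of SWOG intermittent ADT historic cohort".

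The Background (section 2) names the comparator: "We propose using the intermittent ADT cohort of the SWOG trial as a historic comparator of efficacy to this study". It gives one 2-year survival figure from that trial: men with minimal disease "receiving intermittent androgen deprivation had an 85% overall survival". On the grouping it says: "Minimal disease was defined as disease confined to the spine, pelvic bones, or lymph nodes". Men with visceral metastases or other bony sites were classed as extensive.

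Earlier in the same section the protocol states: "Men with five or fewer prostate cancer bone metastases noted on initial bone scan have a 94% 2-year survival rate". Five bone metastases is also this trial's limit (5.1.1, 5.2.3). Inclusion criterion 5.1.5 requires "Life expectancy of at least 2 years". Section 6 describes the participants as M0 at presentation, with oligometastatic disease developing after definitive treatment.

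Section 11 evaluates the secondary endpoints descriptively and analyses survival by Kaplan-Meier with 95% confidence intervals. It gives no test, threshold or success rule for survival and does not name the type of interval.

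**The concern.** The comparator and the enrolled men differ on the feature the protocol itself treats as prognostic, the number of bone lesions. The Background says that men with five or fewer lesions survive significantly longer than men with more. The SWOG minimal-disease group has no lesion cap in the description given, and the whole intermittent arm also includes extensive disease.

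The protocol's two reference figures are 9 points apart (94% − 85%) and are not reconciled. If the higher one is nearer the truth for these men, a regimen with no effect on survival would usually yield an estimate above the only SWOG figure available. A single-arm study of 20 men cannot separate that from a treatment effect. What is at stake is the survival statement in the final report. The primary analysis and the sample size do not depend on it.

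**Working it through.** **The plan's own figures.** None is given for survival. The two calculations in section 11 concern freedom from systemic therapy, and both reproduce with exact binomials at n = 20:
- Primary: P(X ≥ 2) = 0.931 at 20% free of therapy and 0.017 at 1%, matching the stated 93% power at one-sided 0.05.
- Secondary test against SWOG: 9 or more of 20 has probability 0.802 at 52% free and 0.019 at 22%, matching the stated 80%.

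**Inputs for survival.** n = 20 (4.2, section 11); SWOG minimal-disease figure 85% and figure for five or fewer lesions 94% (both section 2). Assumptions: 2-year status is known for all 20, and treatment has no effect on survival. Since 94% may not carry over to these men, the true rate is varied from 85% to 94%.

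**Step 1: what counts as above 85%.** 0.85 × 20 = 17, so an estimate above 85% needs 18 or more alive. At a true 94% the expected number is 0.94 × 20 = 18.8.

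**Step 2: chance of that with no treatment effect.** P(X ≥ 18) = C(20,18)p¹⁸(1−p)² + 20p¹⁹(1−p) + p²⁰. At p = 0.94 this is 0.2246 + 0.3703 + 0.2901 = 0.885.

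| True 2-year survival | P(observed > 85%) |
|---|---|
| 94% | 0.885 |
| 92% | 0.788 |
| 90% | 0.677 |
| 88% | 0.563 |
| 85% | 0.405 |

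Even where the true rate equals 85%, the estimate exceeds it four times in ten. At 90% it does so about two times in three.

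**Step 3: what the planned interval would show.** Section 11 leaves the interval type open, and near 100% survival the choice decides the message. With 19 of 20 alive and no censoring:
- Plain Greenwood: SE = √(0.95 × 0.05 / 20) = 0.0487; lower limit 0.95 − 1.96 × 0.0487 = 0.854. The upper limit exceeds 1.
- Log-log: 0.695 to 0.993.
- Exact (Clopper-Pearson): 0.751 to 0.999.

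So plain Greenwood appears to exclude 85% and the other two do not. At a true 94%, 19 or 20 survivors occur with probability 0.3703 + 0.2901 = 0.660. With 20 of 20 alive the Greenwood variance is zero and the log-log transform is undefined; the exact interval has lower limit 0.025^(1/20) = 0.832.

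**The case against.** The strongest reply is that survival is a secondary, descriptive endpoint. Section 11 attaches no test or success rule to it, and section 2 lists SWOG among comparators outside the primary aim. Every single-arm phase IIa study has imperfect historical controls. This stands as a limit on the harm. It does not remove the comparison in 1.2.5, or the sentence in 4.1 that says the study will test for improved survival and so disagrees with section 11.

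The second reply is that 94% is no better matched than 85%. It refers to the initial bone scan, whereas these men were M0 at presentation, and the protocol does not say how the men behind it were treated. The SWOG mismatch also cuts both ways: a man here with a single lesion outside the spine and pelvis would have counted as extensive there. This stands too, and is why the result is given over a range of true rates.

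Stronger readings that a reader might infer, and that the documents do not support:
- That 85% is the fixed benchmark. Sections 1.2.5 and 4.1 name the intermittent cohort and give no number; 85% belongs to a subgroup.
- That selection alone would certainly produce an apparent gain. The chance depends on the unknown true rate. The 2-year life-expectancy criterion may add to it, but SWOG's own criteria are not given.
- That no result could exclude 85%. This holds for exact two-sided 95% intervals. It fails for plain Greenwood at 19 of 20, and for an exact one-sided 0.05 test at 20 of 20 (0.85²⁰ = 0.039).

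**Conclusion.** The point holds as a mismatch of comparator and an unsupported aim. The SWOG group and figure for the survival comparison are not identified, the cohort is not matched on lesion count, and the one figure supplied lies 9 points below the protocol's own figure for the same lesion limit. With no treatment effect, the observed rate would exceed 85% with probability 0.405 to 0.885 as the true rate runs from 85% to 94%. An apparent gain could therefore arise from population differences alone.

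This rests on complete 2-year follow-up of 20 men and on taking 85% as the figure a reader would use. If the whole intermittent arm is meant, its 2-year survival is not given and the size of the problem cannot be computed from the documents. The upper end of the range also requires that 94% carries over to men who were M0 at presentation, which the documents do not establish. Because the endpoint is secondary and descriptive, the matter should be corrected but does not threaten the primary analysis.

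**What to change.** - **Section 4.1:** delete the aim of improving survival over the SWOG cohort, so that the section agrees with the descriptive analysis in section 11.
- **Objective 1.2.5:** reword to estimate 2-year overall survival with its 95% confidence interval, with no claim of improvement over SWOG.
- **If reference figures are shown:** identify the SWOG group; set 85% and 94% side by side; state that one is defined by site and the other by lesion count on the initial bone scan, while these men were M0 at presentation; and note the life-expectancy criterion in 5.1.5.
- **Section 11:** name a confidence-interval method that is valid near 100% survival, exact or log-log and not plain Greenwood. State that the exact interval applies if there are no deaths, since log-log is then undefined. The exact interval requires known 2-year status for each man.

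The cost is wording only: no patients, visits or data are added. The sponsor gives up a statement of superior survival over SWOG.

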1.2.6 Evaluate CTCAE version 4.0 toxicities in the study population
Endpoint: Patients will be monitored for adverse events related to Radium-223 and EBRT using CTCAE criteria.

1.3 Exploratory Objectives

1.3.1 Evaluate whether a commercially available cell-cycle progression gene assay (Myriad CCP) performed on the original prostate biopsy or surgical pathology specimen correlates with biochemical or clinical progression free survival in the study population.

1.3.2 Evaluate whether a commercially available homologous recombination DNA repair assay correlates with biochemical or clinical progression free survival in the study population (Myriad HRD).

2 BACKGROUND

Background: Prostate cancer is the most commonly diagnosed cancer in the United States and second leading cause of cancer death. At diagnosis, approximately 10% of men will have bone metastases identified on technetium bone scan [1]. These bone metastases can result in skeletal related events (SREs) causing substantial morbidity [2]. Men with five or fewer prostate cancer bone metastases noted on initial bone scan have a 94% 2-year survival rate, and a significantly favorable overall survival when compared to those with more lesions [3]. The current standard of care for men with overt metastatic disease is immediate androgen deprivation therapy (ADT) [4]. Long term androgen deprivation therapy results in a significant decrement in quality of life[5] and a host of unfavorable side effects including but not limited to loss of libido, lack of energy, difficulty concentrating, hot flashes, decreased bone density, decreased muscle mass, and increased risk of heart attack and stroke. Although ADT will delay the appearance of tumor related symptoms in metastatic patients, there are no data that it prolongs overall survival[4]. Developing novel strategies to control metastatic prostate cancer with side effect profiles superior to that of ADT or other approved systemic agents is highly desirable. External beam radiation treatment is effective at controlling both primary and metastatic prostate cancers, and Radium-223 has demonstrated a survival benefit in castrate-resistant prostate cancers. Both forms of therapy have been shown to palliate painful bony lesions.

Rationale for the combination of Radium-223 and External Beam Radiation: Radium-223 is a calcium-mimetic radiopharmaceutical that accumulates in bones and emits alpha radiation from Radium-223 decay and releases relatively high energy with a narrow range (2 to 10 cells)[5]. Following promising results in a phase II trial, the phase III ALSYMPCA trial was conducted in mCRPC with symptomatic bone metastases who either had received or were ineligible for docetaxel [6, 7]. Patients received 6 doses of Radium-223 50 kBq/kg intravenously every 4 weeks. A pre-planned interim analysis showed a significant 2.8-month median OS benefit compared to the placebo arm (14 vs. 11.2 months), which is anticipated to lead to regulatory approval [8]. An updated analysis

showed a further improvement in overall survival to 3.6 months with a hazard ratio of 0.695 (i.e., 30.5% reduction in risk of death) [9]. Moreover, the toxicity profile appeared excellent with grades 3-4 neutropenia in 1.8% and thrombocytopenia in 4% of patients. Reassuringly, long-term, 24-month outcomes in the previous randomized phase II trial showed no increase in hematologic toxicities [6, 7].

Radiotherapy for Oligometastasis: In 1995, Hellman and Weichselbaum coined the term “oligometastases” to characterize a state of limited metastasis in which aggressive local control measures could be potentially curative [10, 11]. This led to the development of prospective clinical trials employing the use of Stereotactic Body Radiotherapy (SBRT) to ablate visible oligometastatic disease with curative intent [12]. This approach has been demonstrated to be safe and effective, with local control rates in the 80% range, and durable progression-free survival rates around 20%. In one of the only trials evaluating the role of SBRT exclusively in 40 patients with bone only metastatic prostate cancer, the actuarial 24-month local tumor control rate was 95.5% as measured by MRI and PET CT imaging and the median initial PSA before treatment was 5.4 ng/dl which dropped to 2.7 ng/dl after 3 months [13]. We propose that the combination of external beam radiotherapy and Radium-223 will be an effective therapy at controlling oligometastatic prostate cancer in hormone-therapy naïve patients.

Comparator Cohort:

At the Huntsman Cancer Institute at the University of Utah, 100% of persons have been started on systemic therapies to treat their metastatic prostate cancer by 15 months of the identification of oligometastasis. The goal of the current study is to assess whether the Radium-223 and EBRT to oligometastatic sites will delay the need to initiate additional antineoplastic systemic therapies by 15 months.

Other Comparators of interest that are not specified as the primary aim:

In 2012 the SWOG cooperative group reported mature results of a randomized trial evaluating continuous versus intermittent androgen-deprivation therapy in men with hormone-naïve metastatic prostate cancer [14]. This trial was pivotal in cementing the care standard of immediate and continuous androgen deprivation in men with hormone-naïve metastatic prostate cancer, as a median survival benefit was noted over the intermittent cohort despite the fact that, statistically speaking, inferiority of intermittent therapy was not proven nor disproven. Men on the intermittent therapy arm did have significant improvement in quality of life domains. Notably, 78% of persons on the “intermittent” androgen therapy arm had to resume ADT within the first 15 months. Additionally, the investigators of this study classified patients as having “minimal” versus “extensive” disease as an analysis stratification. Minimal disease was defined as disease confined to the spine, pelvic bones, or lymph nodes. Those with visceral metastasis or other bony sites were classified as extensive. At 2 years, subjects with “minimal disease” receiving intermittent androgen deprivation had an 85% overall survival. We propose using the intermittent ADT cohort of the SWOG trial as a historic comparator of efficacy to this study.

Oligometastasis is a limited disease state that some have postulated may be curable. We will use best available ablative therapies to destroy gross tumor, and allow radium-223 to obliterate occult sites of metastasis that cannot be resolved by available imaging modalities. This may lead to delay of initiation of ADT or other antineoplastic systemic therapies, improved QOL, survival benefit, and potential cure.

Reference treatment is the standard of care use of immediate and continuous ADT as well as other reasonable standards of intermittent ADT, or other antineoplastic systemic therapies. Hypofractionated radiotherapy is not routinely used in asymptomatic lesions unless there is risk of impending pathologic injury.

3 DRUG AND RADIATION THERAPY INFORMATION

3.1 Radium Ra-223 (Drug information for Radium-223 taken from the investigators brochure and Xofigo prescribing information.)

3.1.1 Description

Radium Ra-223 dichloride, an alpha particle-emitting pharmaceutical, is a radiotherapeutic drug. Radium Ra-223 dichloride is supplied as a clear, colorless, isotonic, and sterile solution to be administered intravenously with pH between 6 and 8. Each milliliter of solution contains 1100 kBq Radium-223 dichloride (30 microcurie), corresponding to 0.58 ng radium-223, at the reference date. Radium is present in the solution as a free divalent cation. Each vial contains 6 mL of solution (6,600 kBq (178 microcurie) Radium-223 dichloride at the reference date). The inactive ingredients are 6.3 mg/mL sodium chloride USP (tonicity agent), 7.2 mg/mL sodium citrate USP (for pH adjustment), 0.2 mg/mL hydrochloric acid USP (for pH adjustment), and water for injection USP. The molecular weight of Radium-223 dichloride, $^{223}\text{RaCl}_2$, is 293.9 g/mol. Radium-223 has a half-life of 11.4 days. The specific activity of Radium-223 is 1.9 MBq (51.4 microcurie)/ng. The six-stage-decay of Radium-223 to stable lead-207 occurs via short-lived daughters, and is accompanied predominantly by alpha emissions. There are also beta and gamma emissions with different energies and emission probabilities. The fraction of energy emitted from Radium-223 and its daughters as alpha-particles is 95.3% (energy range of 5 - 7.5 MeV). The fraction emitted as beta-particles is 3.6% (average energies are 0.445 MeV and 0.492 MeV), and the fraction emitted as gamma-radiation is 1.1% (energy range of 0.01 - 1.27 MeV).

NIST Standardization

The quantification of Radium-223 radioactivity is based on the primary standardization performed by the US NIST. National Institute of Standards and Technology prepares the standard reference material (SRM) using an official dial setting (primary standardization) as published (as provided in the Investigator Brochure). The NIST SRM is used to calibrate the instruments in production and

quality control for both the drug substance and drug product. Additionally, the NIST SRM is used to prepare the NIST traceable Ra-223 reference materials which are then sent to the end users (e.g., nuclear medicine laboratory physicians or technicians) for dial-setting of their dose calibrators, to allow verification of the patient dose.

In 2014, NIST performed a re-assessment of the primary standardization based on preliminary information suggesting a potential discrepancy of approximately 8-10% between the published NIST primary standardization (as provided in the Investigator Brochure) and results obtained by other national metrology institutes (United Kingdom, Germany, Japan). After completion of the re-assessment, NIST reported their findings (as provided in the Investigator Brochure) and had issued a revised NIST SRM in 2015. The discrepancy in the NIST standardization was determined to be -9.5% between activity values obtained using the old reference standard relative to the new primary standardization. Consequently the current numerical values need to be corrected by approx. + 10.5%.

The current NIST standard for Radium-223 dichloride remained in effect until 4/25/16. As of that date the FDA approved the regulatory variation submitted for Radium-223. The change in the numerical description of the patient's dose, product strength and labeled vial activity does not impact the safety or efficacy of Radium-223. The change in the NIST Radium-223 standard has no impact on subjects; dose subjects are receiving, and will continue to receive. Subjects will receive the same actual dose and volume that was studied in Study 15245 (BC1-06 dosimetry study) and is associated with the proven safety and efficacy of Radium-223 dichloride, though the stated nominal radiation dose received is being updated to reflect the new standard. The current dose regimen of Radium-223 is 55 kBq (1.49 microcurie) per kg body weight.

